16.1.4.4. Proportion of Subjects Converted from Abnormal to Normal

To evaluate whether gantenerumab can decrease the accumulated amyloid plaque from abnormal level to normal level, the threshold of 1.25 will be used to define normal level vs abnormal level at the OLE baseline and at each post-baseline visit. A PiB-PET SUVR >1.25 is considered abnormal while a PiB-PET SUVR ≤ 1.25 is considered normal. A shift from OLE baseline to

Author: [REDACTED]

Version Number:

7

Version Date:

07Dec2023

Template No.: CS TP BS016 Revision 6

Reference: CS WI BS005

Effective Date: 02Dec2019

each post-baseline visit, where missing values are replaced using last observation carried forward (allowing the baseline value to also be carried forward), and to the last post-baseline OLE measurement will be provided along with a corresponding Fisher's exact test. A supportive analysis of shifts at each post-baseline visit without carrying forward values will also be provided. This analysis will be conducted for the OLE Gant mITT population.

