5.3. MODIFIED INTENT-TO-TREAT [mITT]

The mITT analysis populations include all enrolled mutation positive subjects who receive any treatment post-baseline and have at least one assessment for the analysis primary parameter (PiB-PET SUVR for final analysis, CDR Global for both the interim analysis and the final analysis) prior to the associated treatment period (as a baseline assessment) and a post-baseline assessment. For analysis of clinical/cognitive endpoints or non-PET biomarker endpoints, the mITT population identified based on CDR Global should be used.

Author: [REDACTED]

Version Number:

7

Version Date:

07Dec2023

[figure not shown]
Template No.: CS_TP_BS016 Revision 6

Reference: CS_WI_BS005

Effective Date: 02Dec2019

There will be three separate mITT populations:

1. OLE Gant mITT: Any subjects in the OLE meeting mITT criteria using OLE baseline (defined as the last assessment time for the analysis primary parameter prior to the first dose of OLE treatment) as the baseline reference point. Refer to figure below where the data contributing to the population is highlighted in yellow (and denoted with '(Tx)') for the OLE period, regardless of double-blind treatment, with controls (further described in [Section 5.4](#)) highlighted in green from both placebo double-blind only subjects and matched controls from DIAN-OBS.

2. OLE Gant All Gant exposure mITT: Any subjects treated with gantenerumab in both the DB and OLE who meet mITT criteria using DB baseline as the baseline reference point. Refer to figure below where the data contributing to the population is highlighted in yellow (and denoted with '(Tx)') for subjects treated with gantenerumab in both DB and

Author: [REDACTED]

Version Number:

7

Version Date:

[figure not shown]
07Dec2023

Template No.: CS_TP_BS016 Revision 6

Reference: CS_WI_BS005

Effective Date: 02Dec2019

OLE, with main set controls (further described in [Section 5.4](#)) highlighted in green from both placebo double-blind only subjects and matched controls from DIAN-OBS, and an additional set of extended controls (using DB and OLE baseline values for double-blind placebo subjects entering OLE) in a different shade of green to be added to the main set controls to form a second set of controls for the population.

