7.3. MISSING DATA

There will be no imputation of missing data. Handling of missing data for specific efficacy endpoints is detailed in [Sections 16.1.2](#) and [16.2.2](#).

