16.1.2. MISSING DATA METHODS FOR PRIMARY EFFICACY VARIABLE(S)

There will be no missing data imputation for the primary efficacy variable.

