17. SUBSET OF ANALYSES AT THE INTERIM

The two objectives of the interim analysis are to determine if gantenerumab OLE treatment results in clinical benefit and determine the extent of amyloid removal compared to the double-blind period. The primary analyses for the interim will be the primary analysis of CDR Global

Author: [REDACTED]

Version Number:

7

Version Date:

07Dec2023

Template No.: CS TP BS016 Revision 6

Reference: CS WI BS005

Effective Date: 02Dec2019

(in Section 16.2.3.2) and CDR-SB (in Section 16.2.3.1) applied to subjects who are asymptomatic at baseline for the All Gant Exposure mITT and main set controls.

The following subset of analyses will be conducted separately for baseline asymptomatic and baseline symptomatic subjects, except where noted for select imaging and fluid biomarker analyses, at the interim analysis and additional exploratory analyses will be conducted as needed, noting that focus will be on Year 2 findings in the absence of Year 3 findings, with any imputation for Year 3 excluded. These analyses will be conducted for the each of the three mITT populations and controls as specified for each model, unless the associated section describes the analysis as being conducted on select mITT populations, noting that when multiple models are described within a section, only the first one will be conducted for the interim unless otherwise specified. By-visit descriptive statistics during OLE will be displayed, overall and by OLE baseline symptomatic status, for each associated parameter, including each component of the OLE cognitive composite.

[REDACTED] [REDACTED]

Author: [REDACTED]

Version Number: 7

Version Date: 07Dec2023

Template No.: CS_TP_BS016 Revision 6

Reference: CS_WI_BS005

Effective Date: 02Dec2019

Table B: Interim Analysis Models

Endpoint	Analysis Tier and Statistical Method	Objective
CDR Global	Primary: 16.2.3.2: Cox proportional hazards time to first progression	To evaluate whether the treatment delays the disease progression
	Sensitivity: 16.2.4.2 (third paragraph): post-baseline PiB-PET SUVR normal	To evaluate whether normal / abnormal amyloid levels are associated with lower risk of first progression (delay of disease progression) in CDR Global compared to all controls
	Sensitivity: 16.2.4.1.1 (third paragraph): comparison to concurrent and non-concurrent controls	To evaluate whether the treatment delays the disease progression in CDR Global compared to the concurrent and non-concurrent controls

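### The SAP rules out imputing PiB-PET but carries scans forward in the amyloid-normalisation table, and the interim's Year 3 exclusion is not extended to the final analysis of an extension that stopped early

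*SAP*

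**What the plan says.** **General rule.** SAP 7.3: "There will be no imputation of missing data". It refers the reader to 16.1.2 and 16.2.2 for endpoint-specific handling.

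**Rule for PiB-PET SUVR.** SAP 16.1.2: "There will be no missing data imputation for the primary efficacy variable". No exception is given.

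**The normalisation analysis.** SAP 16.1.4.4 sits under the supplementary analyses of that same variable. It classifies each scan against SUVR 1.25 in the OLE Gant mITT population and tabulates shifts from OLE baseline in three ways:
- to each visit with carry-forward: "missing values are replaced using last observation carried forward (allowing the baseline value to also be carried forward";
- to the final available scan: "to the last post-baseline OLE measurement will be provided";
- to each visit as observed: "A supportive analysis of shifts at each post-baseline visit without carrying forward values will also be provided".

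**The interim.** SAP 17: "focus will be on Year 2 findings in the absence of Year 3 findings, with any imputation for Year 3 excluded". No equivalent sentence covers the final analysis.

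**Population.** For the final PET analysis, SAP 5.3 requires "at least one assessment for the analysis primary parameter (PiB-PET SUVR for final analysis", both before treatment and after baseline.

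**Early stop.** The version 7 revision history records that the interim led to early termination of the OLE, and that the pandemic left substantial PET data missing.

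**The concern.** Carry-forward is imputation, so 16.1.4.4 conflicts with 7.3 and 16.1.2. A reader who follows the reference from 7.3 to 16.1.2 would conclude that every PiB-PET result is observed data.

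The practical issue is the Year 3 row of the final by-visit table. Section 17 recognises that Year 3 cells should not be filled when that visit has not happened. Because the OLE was then stopped, some participants could never reach Year 3, yet at the final analysis 16.1.4.4 fills their Year 3 cells from an earlier scan. Of the two by-visit tables, the one with carry-forward leads and the one without is called supportive.

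The proportion moved from abnormal to normal is the result closest to the OLE's stated objective of continued or complete plaque removal. A proportion labelled Year 3 that largely describes Year 1 or Year 2 could be quoted as a three-year clearance rate.

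**Working it through.** **1. What the plan expected at Year 3.** Protocol Appendix 3, section 4.1.2 assumes 60 to 90 enrolled and 5% annual dropout. 60 × 0.95³ = 51.4 and 90 × 0.95³ = 77.2, matching the stated 51 and 77. Planned loss by Year 3 is 1 − 0.95³ = 14.3%. Early termination raises the share without a Year 3 scan above this by an amount the documents do not give.

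**2. Which scans can fill the Year 3 cell.**
- Year 3 is Week 156 and annual windows are ±182 days (SAP 6.4). The window opens at day 156 × 7 − 182 = 910, that is Week 130. A participant last scanned before then has the Year 3 cell filled from an earlier scan. Early-termination scans inside the window count as Year 3 (SAP 6.3).
- The first annual OLE visit is at Week 48 (Protocol Appendix 3, 1.13.1) and titration takes 15 months (1.5.2.1), about 15 × 52/12 = 65 weeks. A scheduled Year 1 scan therefore precedes the target dose.
- Baseline: every member of the final PET mITT has a post-baseline PiB scan, so carry-forward to Year 3 normally starts from that scan. The exception is a sole scan before the Year 1 window opens (48 × 7 − 182 = day 154, about Week 22). Baseline carry-forward bears mainly on the Year 1 row, or on Year 2 when the first scan is later still. It also bears on the interim, where mITT membership rests on CDR Global.
- When scans fall inside the windows, the carried-forward Year 3 row is in effect the last-scan shift under another label.

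**3. Size of the error.** Let m be the share without a Year 3 scan, p3 the true Year 3 conversion (taken as equal in those with and without the scan), and pL the conversion at the last earlier scan among those missing Year 3.

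Reported = (1 − m) × p3 + m × pL, so error = m × (pL − p3).

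None of m, p3 and pL is in the documents. With p3 = 50% as an assumption:

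| m | pL = 30% | pL = 50% | pL = 60% |
|---|---|---|---|
| 0.15 | 47% | 50% | 51.5% |
| 0.50 | 40% | 50% | 55% |
| 0.80 | 34% | 50% | 58% |

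For example, 0.50 × 50% + 0.50 × 30% = 40%. The first m is close to planned dropout; the others stand for early termination.

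**4. A simulated check under steady decline.** Assumptions: baseline SUVR mean 2.0 and SD 0.6; mean change −0.473 over three years (the protocol's projection) spread evenly by year; Year 3 scans missing at random. True Year 3 conversion was about 29%. Carry-forward gave 27 to 28%, 22 to 23% and 18 to 19% with 15%, 50% and 80% missing at Year 3. Observed values stayed at about 29%. No baseline scan was carried to Year 3. This shows understatement when decline continues, but continued decline was an input.

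**The case against.** The strongest points on the other side:

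- **The analysis is supplementary.** The primary objective is tested by the MMRM on continuous SUVR in 16.1.3, which carries nothing forward. No decision rule rests on the shift table. This stands, and it limits the weight of the point.
- **The alternatives are already planned.** The last-scan shift is in the same sentence as the carried-forward table, and the observed-value table follows. This also stands. What remains is the label on the Year 3 row, the order of prominence and the conflict with 7.3 and 16.1.2.
- **Section 17 answers an interim question.** Its exclusion is tied to the absence of Year 3 data at the interim cut, so not repeating it is an omission and not a contradiction. Agreed, but version 7 followed the early stop, when the same reason applied to many final Year 3 cells.
- **Carry-forward can be conservative.** In an uncontrolled extension, counting a participant who dropped out as not normalised guards against overclaiming clearance, while observed-case results may favour completers. This is a fair reason to keep it for participants who discontinued for other reasons. It is weaker for those whose follow-up ended because the sponsor stopped the OLE.

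Two stronger readings are tempting. A reader might infer that Year 3 conversion *is* understated, because Protocol Appendix 3, 1.5.2.2 projects most participants below threshold within two years and full removal in three to four. That is a model projection for continued dosing, against 20 centiloids, with no mapping to SUVR 1.25. The same section reports faster amyloid growth in this population, and if amyloid rises once dosing stops, carry-forward overstates. A reader might also infer that pre-treatment scans populate the final Year 3 row. The population definition in SAP 5.3 all but rules that out.

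**Conclusion.** The point holds in limited form. SAP 16.1.4.4 conflicts with 7.3 and 16.1.2, and the final Year 3 row can present Year 1 or Year 2 scans as Year 3 status for participants who could not reach that visit. Understatement is the likelier direction if amyloid would have kept falling, since scheduled Year 1 scans precede the target dose, but it is not established.

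No single size can be given. Over the assumed range (Year 3 conversion 50%, last-scan conversion 30% to 60%, 15% to 80% unscanned at Year 3), the error runs from 16 points too low to 8 points too high. It is zero if status does not change after the last scan. The primary MMRM conclusion is untouched. The change is worth making because it is cheap and removes a proportion that could easily be misread.

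**What to change.** Amend the SAP as follows:

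1. In 16.1.4.4, extend the Section 17 exclusion to the final analysis: no carry-forward into a visit that a participant could not reach because the sponsor stopped the OLE. Alternatively, label that row as last scan, not Year 3.
2. Show the number actually scanned at each visit.
3. Report the planned observed-value table and last-post-baseline-scan shift alongside the carried-forward table, with at least equal standing at Year 3.
4. In 7.3 and 16.1.2, name 16.1.4.4 as an exception to the no-imputation rule.

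Carry-forward for participants who discontinued for other reasons can stay as a sensitivity analysis.

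Cost: SAP wording and a row of counts; the tables are already planned. The downside is a smaller Year 3 denominator and observed-case results that may favour completers, which is why the sensitivity analysis should be kept.

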The double-blind period had two arms for each study drug, the active study drug and the blinded placebo for that study drug. Subjects were recruited from various sources, i.e., participating DIAN-observational (DIAN-OBS) study sites, DIAN-TU-001 trial sites, DIAN-TU-001 partner sites, the DIAN Expanded Registry study, and families identified by the sites. Mutation positive subjects who signed the informed consent form (ICF), met eligibility requirements and completed all baseline evaluations were randomized in a 3:1 ratio to receive either the active study drug or placebo for the active study drug. Eligible subjects were offered the opportunity to receive active drug for up to 3 years in an open label extension.

Mutation positive subjects who were administered either gantenerumab/placebo to gantenerumab or solanezumab/placebo to solanezumab were allowed to participate in the OLE for gantenerumab. All subjects participating in the OLE will receive gantenerumab. Dosing and titration for the OLE can be found in Section 1.5.2 of Appendix 3 of the protocol.

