5. ANALYSIS SETS

Agreement and documentation of mutation positive subjects included/excluded from each analysis set will be conducted prior to database lock for the OLE. Treatment groups for all analysis sets will be represented as follows and in the given order, noting that “Double-Blind Treatment Arm” will be displayed above the individual treatment columns:

Author: [REDACTED]	Version Number:	7
	Version Date:	07Dec2023
Template No.: CS_TP_BS016 Revision 6	Reference:	CS_WI_BS005
Effective Date: 02Dec2019		

Copyright © 2009, 2010, 2012, 2016, 2018, 2019 [REDACTED] All rights reserved. The contents of this document are confidential and proprietary to [REDACTED] Holdings Inc. and its subsidiaries. Unauthorized use, disclosure or reproduction is strictly prohibited.

- Placebo
- Solanezumab
- Gantenerumab
- Total

A set of controls will be used for efficacy analysis. The control groups are identified in the figures within [Section 5.3](#) and are described within [Section 5.4](#).

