7. TABLE AND LISTING OUTPUT CONVENTIONS

General:

- The first row in the body of the table or listing should be blank.
- The left-hand column should start in column 1. No indenting or centering of the output should occur.
- Rounding should be done with the SAS function ROUND.
- Numbers in tables should be rounded, not truncated.
- Alphanumeric output should be left aligned.
- Numbers should be decimal point aligned.
- Whole numbers should be right aligned.
- Text values should be left aligned.
- The first letter of a text entry should be capitalized.
- Listings of adverse events, concomitant medications, injection site reactions etc. should be sorted in chronological order, with earliest event or medication coming first.
- The treatment column order should be Placebo, Solanezumab, Gantenerumab, Total, with all columns other than Total having a value of Double-Blind Treatment Arm that is a merged field over the treatment group names.
- If possible, include 100% frequencies in the table shell, so that it is clear what the denominator is for percentage calculations.
- All listing outputs should be sorted (preferably by Subject Number) and will not reference double-blind treatment.
- Do not use superscripts and subscripts.
- Exponentiation will be expressed using a double asterisk, i.e., mm³ will be written as mm**3.

Author: [REDACTED]

Version Number:

7

Version Date:

07Dec2023

Template No.: CS_TP_BS016 Revision 6

Reference: CS_WI_BS005

Effective Date: 02Dec2019

- The width of the entire output should match the linesize.

Univariate Statistics:

- Statistics should be presented in the same order across tables (i.e., n, Mean, SD, Median, Minimum, Maximum).
- Table statistics should line up under the N part of the (N=XXX) in the table header. All decimal points should line up. If the minimum and maximum are output on one line as Minimum, Maximum then the comma should line up with the decimal point.
- If the original data has N decimal places, then the summary statistics should have the following decimal places:

Minimum and maximum: N

Mean and median: N + 1

SD or SE: $N + 2$

Frequencies and percentages (n and %):

- Percent values should be reported inside parentheses, with one space between the count and the left parenthesis of the percentage. Parentheses should be justified to accept a maximum of 100 as a value and padded with blank space if the percent is less than 100. An example is given below:

77 (100.0%)
50 (64.9%)
0 (0.0%)

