9. PROGRAMMING INSTRUCTION

Programming instructions must appear in blue font at the end of each table or listing shell.

Author: [REDACTED]

Version Number:

7

Version Date:

07Dec2023

Template No.: CS_TP_BS016 Revision 6

Reference: CS_WI_BS005

Effective Date: 02Dec2019

Programming instructions, where necessary, should follow the table or listing shells in blue font, beginning with the words “Programming Note” followed by a colon. These include notes on the output, reminders of how to handle missing values, repeat shells for similar tables etc.

DATES & TIMES

Depending on data available, dates and times will take the form yyyy-mm-ddThh:mm:ss.

SPELLING FORMAT

English US.

PRESENTATION OF TREATMENT GROUPS

For tables, treatment groups will be represented as follows and in the given order, noting that “Double-Blind Treatment Arm” will be displayed above the individual treatment columns:

- Placebo
- Solanezumab
- Gantenerumab
- Total

PRESENTATION OF VISITS

For outputs, OLE visits will be represented as follows and in that order (Note: refer to protocol for full list of OLE visits), noting that listings will display visits (including unscheduled visit) in date order:

Long Name (default)	Short Name
Baseline (OLE Visit 1)	BL (V1)
Week 4 (OLE Visit 2)	W4 (V2)
Week 8 (OLE Visit 3)	W8 (V3)
...	...
Week 48/52 (OLE Visit 14) *Note: due to a protocol amendment, assessments for year 1 occurring at either week 48 or week 52 will be displayed with the format above	W52 (V14)
...	...
Week 156 (Visit 40)	W156 (V40)
Early Termination	ET
Safety MRI 1 (120 mg)	OSM1
...	...
Safety MRI 11 (stable dose 5 MRI)	OSM11

Summaries and/or models including external and/or double-blind data may display timepoints based on the anticipated duration from treatment start or observational period start, such as Month 6 or Year 1, rather than using visit identifiers.

Author: [REDACTED]

Version Number:

7

Version Date:

07Dec2023

Template No.: CS_TP_BS016 Revision 6

Reference: CS_WI_BS005

Effective Date: 02Dec2019

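### SAP 16.1.4.4 attaches a Fisher's exact test to the abnormal-to-normal amyloid shift without naming the groups, and neither the paired table nor the default arm columns lets that test show conversion

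*SAP*

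**What the plan says.** The stated aim of SAP 16.1.4.4 is "To evaluate whether gantenerumab can decrease the accumulated amyloid plaque from abnormal level to normal level". Each subject is classed as normal or abnormal at OLE baseline and again at each later visit, with a cut at 1.25. The shift to each visit (carrying the last value forward, baseline included) and to the last OLE scan "will be provided along with a corresponding Fisher's exact test". On the population it says: "This analysis will be conducted for the OLE Gant mITT population". It adds: "A supportive analysis of shifts at each post-baseline visit without carrying forward values will also be provided". It gives no rows, columns or comparison groups for the test.

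Other parts of the SAP bear on what the groups might be:

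- Section 3.1: "All subjects participating in the OLE will receive gantenerumab".
- Section 5: "Treatment groups for all analysis sets will be represented as follows and in the given order". The list that follows is the prior double-blind arm (placebo, solanezumab, gantenerumab) and a total. Appendix 1 repeats this: "The treatment column order should be Placebo, Solanezumab, Gantenerumab, Total", and "For tables, treatment groups will be represented as follows and in the given order".
- Section 5.4.6 sets the OLE Gant mITT against the main set controls as a general rule.
- Section 17, Table B, repeats the Fisher test for the interim. Its objective is whether treatment is associated with an abnormal-to-normal shift, and it names no comparator, although many other rows of that table do.
- Section 8 refers to output templates, which are not in the documents reviewed.

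**The concern.** A shift table cross-classifies the same people twice. Fisher's exact test on that table asks whether later status depends on earlier status. If the drug does nothing, everyone keeps their status, dependence is perfect and p is tiny. If the drug clears everyone, later status no longer varies and p is 1. The p-value then runs against the drug effect.

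With prior double-blind arm as the columns, the groups are independent and the test is legitimate. But every column receives gantenerumab in the OLE, so the test can only show that arms differ.

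Either way, a p-value would sit beside a table about amyloid normalisation, and readers would take it as evidence for or against conversion.

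**Working it through.** **Inputs.** The documents state no figure for this test and no count of subjects who are PiB-normal at OLE baseline, so the splits below are assumptions. The first uses the low end of the expected three-year sample in protocol Appendix 3, section 4.1.2: 60 × 0.95³ = 51.4 and 90 × 0.95³ = 77.2, which matches the 51 to 77 stated there. Smaller splits are included because the OLE ended early and the SAP version history reports substantial missing PET data. Tests are two-sided (SAP 6.5).

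**Reading 1: baseline status by later status.** Let A be abnormal at baseline, B normal at baseline, k the number converting, with no reversions. With margins fixed, the probability of the observed table is C(B+k, B) / C(A+B, B), where C(n, r) is the binomial coefficient. Fisher's p sums this and all tables no more probable.

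For A = 41, B = 10:

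- k = 0: 1 / C(51,10) = 7.8e-11, which is also the p-value.
- k = 20: C(30,10) / C(51,10) = 0.0024; two-sided p = 0.0031.
- k = 33: C(43,10) / C(51,10) = 0.15; two-sided p = 0.33.
- k = 41: p = 1.

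Other splits behave the same way:

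| A / B | nobody converts | about half | about 80% | all |
|---|---|---|---|---|
| 41 / 10 | 7.8e-11 | 0.0031 (20) | 0.33 (33) | 1 |
| 32 / 8 | 1.3e-8 | 0.013 (16) | 0.32 (26) | 1 |
| 24 / 6 | 1.7e-6 | 0.057 (12) | 0.55 (19) | 1 |
| 27 / 3 | 2.5e-4 | 0.24 (14) | 1 (22) | 1 |

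If nobody is normal at baseline, one row is empty and p = 1 at every conversion rate. With 41/10 and one reversion, p is 3.3e-9, 0.030, 0.67 and 0.20 at 0, 20, 33 and 41 conversions, so the smallest p still falls at no conversion.

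**Reading 2: prior double-blind arm by converted yes/no.** Take three arms with 11, 11 and 10 baseline-abnormal subjects (assumed), and the exact 3×2 test:

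- 0/0/0 converting: p = 1.
- 9/9/8 converting: p = 1.
- 11/11/10 converting: p = 1.
- 3/3/8 converting: p = 0.025, which shows a difference between arms and nothing more.

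**Reading 3: treated against controls.** With 41 baseline-abnormal treated subjects and an assumed 10 to 80 baseline-abnormal controls, none converting, 20/41 gives p from 0.004 to 8e-12. This comparison could address the aim, but 16.1.4.4 does not write it.

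**The proposed replacement.** The exact (Clopper-Pearson) 95% limits for k of n are the 2.5% quantile of Beta(k, n−k+1) and the 97.5% quantile of Beta(k+1, n−k):

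- 33/41 = 80% (65% to 91%)
- 26/32 = 81% (64% to 93%)
- 19/24 = 79% (58% to 93%)

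Exact McNemar uses only the subjects who change status. With k conversions and no reversions (k ≥ 1), p = 2 × 0.5^k. That is 0.063 at k = 5 and 0.031 at k = 6, and p is 1 at k = 0. It moves in the right direction but takes no account of the denominator, so the proportion and its interval should be the main result.

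**The case against.** The strongest counter-case is that the comparison is merely unspecified. The templates in section 8 may define the table, and nothing in the SAP states the paired reading outright. The default arm columns make Fisher a valid test, and response by prior arm is a question the SAP raises for this endpoint in 16.1.4.1. Section 5.4.6 applies controls to this population generally. 16.1.4.4 does not exclude them, as 16.1.3 does, and the Table B objective could fit a treated-versus-control test.

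Part of this stands. The templates were not available, so which table will be run is not known. The arm comparison is valid as a comparison of arms, but it does not answer the question 16.1.4.4 poses.

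The controls reading is not established. The section is written in terms of OLE baseline and OLE scans, which controls do not have. Section 17 uses controls only where a model specifies them, and the Table B row names none. Section 16.2.4.1.1 does classify controls by their own baseline and last PiB value, so such a comparison could be written; here it has not been.

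Two further points are fair. The practical impact is small, since the shift counts are shown anyway. And version 7 of the SAP follows the interim, so a change of test now should be labelled as such.

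**Conclusion.** The concern holds. The section names no groups. On the most direct reading the p-value runs against conversion, and on the SAP's default columns it does not bear on conversion. The exact p-values depend on assumed baseline splits, but without reversions the direction does not: when some subjects are normal at baseline, p is smallest when nobody converts and 1 when everybody does.

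It should be fixed, but its reach is limited. The analysis is supplementary, has no decision rule, and leaves the primary MMRM untouched. The interim is complete and led to early termination, so the correction is for the final analysis. Any Fisher p-value already produced under Table B should be read with this in mind.

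A minor wording point: 16.1.4.4 carries values forward while 7.3 and 16.1.2 say nothing is imputed. Carrying forward counts as unchanged anyone whose last available status equals baseline. The observed-data version already planned covers this.

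**What to change.** In SAP 16.1.4.4, for the final analysis, replace the Fisher clause with wording such as:

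> Among subjects with OLE-baseline PiB-PET SUVR >1.25, the proportion with SUVR ≤1.25 at each OLE visit and at the last OLE scan will be presented with an exact (Clopper-Pearson) 95% confidence interval. Any test of the within-subject shift will be the exact McNemar test.

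Keep Fisher only for a named comparison of independent groups, restricted to baseline-abnormal subjects. Examples are prior double-blind arm, or controls with their own baseline and follow-up scan defined. State that the change was made after the interim. Note the carry-forward rule as an exception in 7.3 and 16.1.2. The Table B entry can stay as it is.

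The cost is two sentences, one procedure option, a short note on timing and one cross-reference. No new data are needed and the completed interim is not changed.
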